## FLE-002 (INSTANT) – Final Analysis

## Statistical Analysis Plan

P 4	C max ≥300	C max ≥300
P 5	C max ≥400	C max ≥400
P 6	C max ≥500	C max ≥500
P 7	C max ≥600	C max ≥600
P 8	C max ≥700	C max ≥700

Analysis will not be performed for the PLS population.

### 9.2.2.2 *Statistical analysis of time-to-conversion to SR from initiation of dosing up to 90 minutes after initiation of dosing*

The Modified ITT Population will be used for this analysis.

The cumulative incidence for the time to conversion from initiation of study medication up to 90 minutes post dose will be determined using the Kaplan-Meier methods. Subjects who converted within 90 minutes post dose due to adjunct medication or procedure are reported as not converted and will not be censored at the time the subject converted due to the adjunct treatment. Results are shown in a Kaplan-Meier curve.

Kaplan-Meier figures will be created for the following:

- A figure with a single curve, showing results of Part C MLS Cohort (Cohort 1).
- A figure with a single curve, showing results of the Pooled MLS Cohort (Cohort 2)
- A figure with a single curve, showing results of the Pooled MLS No Predose Flecainide Cohort (Cohort 3)
- A figure with two curves, for the Pooled MLS Cohort (Cohort 2) and the Pooled MLS No Predose Flecainide Cohort (Cohort 3)

Analysis will not be performed for the PLS population.

### 9.2.2.3 *The proportion of subjects in SR on Day 2*

The Modified ITT Population will be used to determine the proportion of subjects in SR on Day 2. The rhythm status used for the evaluation of this secondary efficacy endpoint is derived from the remote ECG system, in which the subject's heart rhythm is recorded. A subject is considered in SR on Day 2 if the subject's sinus rhythm during the recording is longer in duration (in seconds) than any of the other reported rhythms (refer to SAS section 5.2). The variable is set to missing if no evaluable remote ECG recording is available for analysis.

The proportion is estimated by the number of subjects in SR on Day 2, divided by the total number of subjects with available data. The estimate for the proportion will be reported.

Analysis will be performed for:

## FLE-002 (INSTANT) – Final Analysis

## Statistical Analysis Plan

- the complete Modified ITT population
- mITT subjects whose AF converted to SR by inhaled flecainide within 90 minutes after initiation of dosing (subjects meeting the primary efficacy endpoint)
- mITT subjects whose AF was not converted to SR by inhaled flecainide within 90 minutes after initiation of dosing (subjects not meeting the primary efficacy endpoint)

Analysis will not be performed for the PLS population.

### **9.2.2.4 *The proportion of subjects with reduced or no AF symptoms at 30 minutes post dose***

The Modified ITT Population will be used to determine the proportion of subjects with reduced or no AF symptoms (compared to baseline) at 30 minutes post dose.

The evolution of symptoms (no symptoms, improved, unchanged or worsened) is a categorical variable, a subject is considered to have reduced or no AF symptoms at 30 minutes post initiation of dose (compared to baseline) if the symptoms are reported as either 'no symptoms' or 'improved'.

The proportion is estimated by the number of subjects meeting the endpoint divided by the total number of subjects with available data. The estimate for the proportion will be reported. The variable is set to missing if no information is available.

Analysis will be performed for:

- the complete Modified ITT population
- mITT subjects whose AF converted to SR by inhaled flecainide within 30 minutes post dose
- mITT subjects whose AF was not converted to SR by inhaled flecainide within 30 minutes post dose

Analysis will not be performed for the PLS population.

### **9.2.2.5 *The proportion of subjects with reduced or no AF symptoms at 60 minutes post dose***

The Modified ITT Population will be used to determine the proportion of subjects with reduced or no AF symptoms (compared to baseline) at 60 minutes post dose.

The evolution of symptoms (no symptoms, improved, unchanged or worsened) is a categorical variable, a subject is considered to have reduced or no AF symptoms at 60 minutes post initiation of dose (compared to baseline) if the symptoms are reported as either 'no symptoms' or 'improved'.

## **FLE-002 (INSTANT) – Final Analysis**

## **Statistical Analysis Plan**

The proportion is estimated by the number of subjects meeting the endpoint divided by the total number of subjects with available data. The estimate for the proportion will be reported. The variable is set to missing if no information is available.

Analysis will be performed for:

- the complete Modified ITT population
- mITT subjects whose AF converted to SR by inhaled flecainide within 60 minutes post dose
- mITT subjects whose AF was not converted to SR by inhaled flecainide within 60 minutes post dose

Analysis will not be performed for the PLS population.

### ***9.2.2.6 The proportion of subjects with reduced or no AF symptoms at 90 minutes post dose***

The Modified ITT Population will be used to determine the proportion of subjects with reduced or no AF symptoms (compared to baseline) at 90 minutes post dose.

The evolution of symptoms (no symptoms, improved, unchanged or worsened) is a categorical variable, a subject is considered to have reduced or no AF symptoms at discharge dose (compared to baseline) if the symptoms are reported as either 'no symptoms' or 'improved'.

The proportion is estimated by the number of subjects meeting the endpoint divided by the total number of subjects with available data. The estimate for the proportion will be reported. The variable is set to missing if no information is available.

Analysis will be performed for:

- the complete Modified ITT population
- mITT subjects whose AF converted to SR by inhaled flecainide within 90 minutes post dose
- mITT subjects whose AF was not converted to SR by inhaled flecainide within 90 minutes post dose

Analysis will not be performed for the PLS population.

### ***9.2.2.7 The proportion of subjects who had their AF converted to SR within 90 minutes after initiation of dosing and had no AF recurrence requiring electrical or pharmacological cardioversion or rate control intervention, up to discharge***

The Modified ITT MLS Population will be used to determine this endpoint.

**FLE-002 (INSTANT) – Final Analysis****Statistical Analysis Plan**

This endpoint is derived from the primary efficacy endpoint at 90 minutes after initiation of dosing. The endpoint is met if the subject's AF converts to SR within 90 minutes after initiation of dosing without an alternative therapy and without subsequent AF recurrence up to discharge requiring additional intervention, either by electrical or pharmacological cardioversion or by rate control treatments.

This proportion of subjects that convert to SR without AF recurrence is estimated as the number of subjects who meet the endpoint, divided by the total number of mITT subjects. The estimate for the proportion and its associated 95% Clopper-Pearson CI will be derived.

The requirements for meeting the endpoint are thus as follows:

*- the start time of the conversion of AF to SR is within 90 minutes (including 90 minutes) after the initiation of study drug, AND EITHER*

*-no recurrence of AF occurred between time of conversion and discharge, OR  
-recurrence of AF occurred between time of conversion and discharge but for subject none of the indicated interventions (as reported by investigator) was started between initiation of dosing and discharge.*

Discharge is left to the discretion of the treating physician 90 minutes post dose (-10 minute window).

Additionally, analysis is repeated for the proportion of subjects whose AF converted to SR within 90 minutes post dose.

*No imputation will take place, i.e., the subject is assumed to be free of event (No Conversion, No AF Recurrence, None of the three Interventions) after the time last information is available.*

Analysis will not be performed for the PLS population.

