5.4.2 B - Post-dose regimen therapy and medication

The Investigator may offer an alternative treatment after 90 minutes post dose, within the institutional standard of care and in accordance with Section 5.4.1 B above, to subjects without conversion of AF to SR. The choice of the treatment is guided by subject-specific factors and subject preferences and is left at the discretion of the treating physician and to subject's approval with the exception of sotalol, procainamide or ibutilide, which are not allowed throughout the study. Alternate therapy in accordance with the guidelines above may be given as early 60 minutes pose dose only if deemed medically necessary by the investigator not to wait until 90 minutes post dose; however, IV flecainide and propafenone may not be administered until at least 90 minutes post dose.

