8.0 EU-1 Page: 75 of 117 Version

10.2.1.7 B - The proportion of subjects with reduced or no AF symptoms at 90 minutes post dose

A subject is considered to have reduced or no AF symptoms at 90 minutes post dose based on patient-reported outcomes (reported as either 'no symptoms' or 'improved').

The evolution of symptoms (no symptoms, improved, unchanged or worsened) is a categorical variable that will be summarized by the frequency and proportion of subjects within each category. The estimate for the proportion and its associated 95% Clopper-Pearson CI will be derived.

10.2.1.8 B - Descriptive statistics of proportion of conversion to SR within 90 minutes after initiation of dosing without AF recurrence requiring electrical or pharmacological cardioversion or rate control intervention up to discharge

This endpoint is derived from the primary efficacy endpoint at 90 minutes after initiation of dosing. The endpoint is met if the subject's AF converts to SR within 90 minutes after initiation of dosing without an alternative therapy and without subsequent AF recurrence up to discharge requiring additional intervention, either by electrical or pharmacological cardioversion or by rate control treatments.

The proportion of subjects that convert to SR without AF recurrence is estimated as the number of subjects who meet the endpoint, divided by the total number of mITT subjects. The estimate for the proportion and its associated 95% Clopper-Pearson CI will be derived.

10.2.1.9 B - The proportion of subjects in SR on Day 5

The rhythm status used for the evaluation of this secondary efficacy endpoint is derived from the remote ECG Event Recorder, in which the subject's heart rhythm is recorded. A subject is considered in SR on Day 5 if the remote ECG recording at the intended time shows SR. The variable is set to missing if no evaluable remote ECG recording is available for analysis.

The proportion is estimated by the number of subjects in SR on Day 5, divided by the total number of subjects with available data. The estimate of the proportion and its associated 95% Clopper-Pearson CI will be derived.

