## FLE-002 (INSTANT) – Final Analysis

## Statistical Analysis Plan

Analysis is performed for the mITT population. A Subject meets the endpoint if conversion occurred within 90 minutes after initiation of dosing without the use alternative medication (e.g., IV flecainide and propafenone) or procedures (e.g., ECV). If a subject's conversion status is unknown, then the analysis will assume that the subject did not convert.

The percentage is calculated as:

$$p = 100 * (\text{number of converted subjects} / \text{number of subjects in mITT population})$$

A 90% exact binomial confidence interval will be calculated for the percentage.

No formal testing will take place. Analysis will not be performed for the PLS population.

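### The requirement list in SAP 9.2.2.7 drops the no-alternative-therapy condition, and SAP 9.2.2.2 runs the Kaplan-Meier analysis past its own 90-minute limit (low severity, wording fixes)

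*SAP*

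**What the plan says.** **No-recurrence endpoint (SAP 9.2.2.7).** The section ties the endpoint to the primary one: "This endpoint is derived from the primary efficacy endpoint at 90 minutes after initiation of dosing". Its prose requires that AF "converts to SR within 90 minutes after initiation of dosing without an alternative therapy". Protocol 10.2.1.8 B sets the same condition: "within 90 minutes after initiation of dosing without an alternative therapy and without subsequent AF recurrence up to discharge". The SAP then gives the requirements as a list, presented as following from the prose. Conversion must start "within 90 minutes (including 90 minutes) after the initiation of study drug, AND EITHER" there is no recurrence before discharge, or there is a recurrence but "none of the indicated interventions (as reported by investigator) was started between initiation of dosing and discharge". A second horizon is added: "Additionally, analysis is repeated for the proportion of subjects whose AF converted to SR within 90 minutes post dose".

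**Time to conversion (SAP 9.2.2.2).** The heading ends the analysis at 90 minutes after initiation of dosing, as do SAP 6.2.2 and protocol 10.2.1.3 B. The Kaplan-Meier sentence ends it at 90 minutes post dose. The next sentence, which keeps adjunct-treated converters in the analysis as not converted, uses the same post-dose limit. SAP 3.3 counts post-dose times from the end of study drug administration. SAP 10, which lists departures from the protocol, has no entry for this.

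**The concern.** The list is the part a programmer will code, and it is a different rule from the prose above it. Its no-recurrence branch never asks how the subject converted. SAP 3.1 does not supply the missing condition: it defines conversion and index conversion by rhythm and duration only, and SAP 3.2 treats conversion by study drug, by adjunct medication and by adjunct procedure as separate kinds of index conversion. An endpoint meant to be a subset of the primary endpoint could therefore contain subjects who fail the primary endpoint.

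In 9.2.2.2, an unaided conversion later than 90 minutes after initiation is spontaneous under SAP 3.2 and fails the primary endpoint. Under the Kaplan-Meier sentence it would still be an event if it falls within 90 minutes of the end of dosing. The end of the curve could then exceed the primary proportion without explanation.

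**Working it through.** **1. The clock.** Protocol 5.3.4 B gives two inhalations of 3.5 minutes with a 1-minute break: 3.5 + 1 + 3.5 = 8 minutes. The protocol synopsis (study duration) adds 45 minutes before and 90 minutes after dosing: 45 + 8 + 90 = 143 minutes = 2 h 23 min, which reproduces its stated total.

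**2. Post-dose times on the initiation clock.**

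| Dosing length | 60 min post dose | 90 min post dose |
|---|---|---|
| 8 min (as planned) | 68 min | 98 min |
| 7.5 min (390 s minimum in SAP 8.4 plus the break) | 67.5 min | 97.5 min |

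Protocol 5.3.4 B allows an interruption of more than 30 seconds to be made up. One such interruption gives more than 8.5 minutes of dosing.

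**3. When another therapy can occur.** Protocol 5.4.2 B: "Alternate therapy in accordance with the guidelines above may be given as early 60 minutes pose dose", if medically necessary. That is about 68 minutes after initiation. Protocol 6.2.1 B allows earlier treatment only for an SAE. IV flecainide and propafenone are barred until 90 minutes post dose, and sotalol, procainamide and ibutilide throughout.

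**4. The list read as logic.** Success = (start of conversion ≤ 90 min) AND (no recurrence OR no intervention from initiation to discharge). For a subject converted by permitted alternate therapy at 80 minutes after initiation:

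| Later course | 9.2.2.7 prose | 9.2.2.7 list | Primary endpoint (9.2.1) |
|---|---|---|---|
| No recurrence | Fail | **Success** | Fail |
| Recurrence, nothing more given | Fail | Fail | Fail |

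Only the first row goes wrong. In the second, the intervention check starts at initiation and catches the earlier therapy. The exposed window is 90 − 68 = 22 minutes (22.5 at the shorter dosing length), and 98 − 68 = 30 minutes in the repeat analysis to 90 minutes post dose.

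**5. Kaplan-Meier horizon.** Under SAP 8.5, mITT subjects who stopped dosing early had already converted, so those still at risk completed both stages. The overrun is 98 − 90 = 8 minutes (7.5 at the shorter length, more than 8.5 after a made-up interruption). Holter recording runs to 90 minutes post dose, so conversions in the gap are observed. Adjunct-treated subjects are not censored, so with complete follow-up the curve equals the simple proportion. Example with an assumed 25 conversions in 52 subjects: 25/52 = 48.1% at 90 minutes under either horizon. One unaided conversion in the gap takes the end of the longer curve to 26/52 = 50.0%.

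**6. Shift per subject.** Final cohort sizes are not stated. Protocol 1.4 gives 27 evaluable Part A subjects on FlecIH-103. If Part B reached its planned 25, the pooled cohort is at least about 27 + 25 = 52, and 1/52 = 1.9 points. For the Part C cohort, assumed sizes of 10, 20 or 40 give 10.0, 5.0 or 2.5 points.

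**7. Two clean-up slips.**
- SAP 8.4 takes the end time of the repeat dose from the first-dose record. With planned timings the second stage becomes 3.5 − 4.5 = −1 minute and the total 3.5 − 1 = 2.5 minutes = 150 s, below the 390 s threshold, so subjects dosed exactly as planned would fail.
- In SAP 9.2.4.5 the brackets of p2 divide only N22 by (N − N33). The result exceeds 100% once N11 is 2 or more.

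**The case against.** The best reply is that the intent is not in doubt. The governing sentence stands directly above the list, the list is offered as a restatement, and SAP 6.2.2 says conversion methods will be specified, where applicable, in the overview of tables, figures and listings. This is a fair reason for low severity. It does not make the two rules in the section agree, and that overview is not part of the plan.

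On the curve, 90 minutes post dose is the end of Holter monitoring and recurs in SAP 9.2.2.6, the repeat analysis in 9.2.2.7 and 9.2.5.3, so it may be a chosen display limit. Estimates up to 90 minutes do not change. The SAP is also loose elsewhere: 9.2.2.4 and 9.2.2.5 are headed post dose but define symptom relief post initiation. This limits the consequence, but neither point reconciles the sentence with its own heading, SAP 6.2.2 and the protocol.

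Three qualifications stand:
- The overrun can be 7.5 rather than 8 minutes.
- Dosing stops on telemetry while the analysis uses the Core Laboratory reading, so a subject might stop early on a conversion that is not confirmed. The statement about who is still at risk is therefore not absolute.
- The recurrence branch counts interventions from initiation, whereas the prose concerns interventions required by a later recurrence. A rate-control drug given before an unaided conversion, followed by an untreated recurrence, would still fail the list after the edit below.

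The clean-up slips are minor. The first would show up at once as a negative duration, and the second concerns six handheld echocardiograms.

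**Conclusion.** The point holds, at low severity. SAP 9.2.2.7 contains two different rules, and the codable one can count an alternate-therapy conversion between about 68 and 90 minutes after initiation as a success. SAP 9.2.2.2 contradicts its own heading and the protocol by about 8 minutes. Few subjects are likely to be affected. Each would move a pooled proportion by at most about 1.9 points, assuming at least about 52 pooled mITT subjects; the shift could be larger in the Part C cohort, whose size is not given. The primary endpoint does not change, and the final analysis plans no formal test.

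**What to change.** 1. In SAP 9.2.2.7, make the first listed requirement that the subject meets the SAP 3.2 definition of conversion by the study drug: index conversion within 90 minutes after initiation with no other intervention. Apply the same no-intervention condition to the repeat analysis to 90 minutes post dose. In the same edit, state whether the intervention check in the recurrence branch starts at initiation or at the recurrence.
2. In SAP 9.2.2.2, replace post dose with after initiation of dosing in both sentences.
3. Clean-up: in SAP 8.4 read the end time of the repeat dose from the repeat-dose record, and in SAP 9.2.4.5 write p2 = 100*(N11+N22)/(N−N33).

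The cost is wording changes in two sections and two small corrections. They use definitions and data already in place.

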5.4 B – Non-study therapy

5.4.1 B - Prior and concomitant medication

Prior medications that the subject has taken within 30 days of enrollment and the subject's alcohol use are recorded in the eCRF. Medications taken by the subject prior to enrollment or at any time during the study, including adjunct therapy or medical devices, are regarded as prior and/or concomitant medications/treatments and must be documented on the appropriate pages of the eCRF throughout the study and until the final contact with the subject, i.e., EOS.

If the subject experiences an AE, information on concomitant medications taken within the past 30 days needs to be evaluated when considering causal relationship (Section 17.2.2.3).

The concomitant use of Class II and Class IV AADs, i.e. beta-blockers and calcium channel blockers *is allowed* throughout the study.

Concomitant use of the following therapies is *not allowed*:

- Treatment with Class I and any Class III AADs within 1 week before enrollment (except Amiodarone, which is not allowed within 12 weeks before enrollment);
- Concomitant pharmacological or electrical cardioversion up to 90 minutes post completion of dosing; refer to Section 5.4.2 B;
- Concomitant treatment with sotalol, procainamide or ibutilide is not allowed throughout the study;
- Concomitant systemic treatment with drugs that are strong inhibitors of CYP2D6 (e.g., antidepressants, neuroleptics, propranolol, ritonavir, some antihistamines) or CYP 2D6 inducers (e.g., phenytoin, phenobarbital, carbamazepine);
- Investigational drugs (other than the study treatment regimen)
- Bronchodilators from time of consent to start of inhalation of the study drug

INSTANT Study Clinical Study Protocol

Study no. FLE-002

Version 8.0 EU-1 Page: 52 of 117

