#### 3.2 Methods for Cardioversion

##### Conversion of AF to SR by the study drug

Index Conversion occurred  $\leq 90$  minutes after initiation of study medication, without the administration of any other intervention to induce conversion of AF to SR (e.g., IV flecainide, electrical cardioversion [ECV]).

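### In SAP 9.2.2.7 the rule for converters whose AF recurs counts interventions from the start of dosing, so rate control newly started before the recurrence turns an untreated recurrence into a failure

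*SAP*

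**What the plan says.** The endpoint in the title of SAP 9.2.2.7 is conversion within 90 minutes of starting dosing in subjects who "had no AF recurrence requiring electrical or pharmacological cardioversion or rate control intervention, up to discharge". The text of that section requires conversion with no alternative therapy and "without subsequent AF recurrence up to discharge requiring additional intervention, either by electrical or pharmacological cardioversion or by rate control treatments". Protocol 10.2.1.8 B has the same definition: "without an alternative therapy and without subsequent AF recurrence up to discharge requiring additional intervention".

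The SAP then lists operational requirements, presented as following from that definition. Conversion must start within 90 minutes of initiation of study drug. In addition, either AF did not recur before discharge, or it recurred but "none of the indicated interventions (as reported by investigator) was started between initiation of dosing and discharge". The list does not repeat the no-alternative-therapy condition.

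Four other provisions matter:

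- **Permitted drugs.** Under Protocol 5.4.1 B, "The concomitant use of Class II and Class IV AADs, i.e. beta-blockers and calcium channel blockers" is permitted at any time in the study.
- **Conversion by study drug.** SAP 3.2 rules out only other interventions given to induce conversion. The examples of alternative therapy in SAP 9.2.1 are IV flecainide, propafenone and electrical cardioversion (ECV). Rate control is not named.
- **Recurrence.** SAP 3.1 needs only 1 minute of AF after the index conversion.
- **Declared differences.** SAP section 10, which lists departures from the protocol, does not mention this rule.

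**The concern.** The definition fails a subject only when a recurrence calls for treatment. An intervention begun before the recurrence cannot have been required by it. The listed rule asks for neither a time order nor any link between the two; it asks only whether a listed intervention began somewhere between first inhalation and discharge.

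Rate control is where this bites. It is permitted after T0, it is one of the listed interventions, and it does not cost the subject the primary endpoint. Such a subject can be a primary success, have a short recurrence that nobody treats, and be coded as a failure here. The durable-conversion rate would then partly reflect treatment begun before the recurrence and not the outcome that the endpoint names.

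**Working it through.** No sample size, power or expected rate is stated for this endpoint, so there is no plan figure to reproduce. The check applies the two rules to the same subjects and then scales the effect of one reclassification.

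**Rules compared**

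- Listed rule: a converter with a recurrence before discharge fails if any listed intervention starts between time 0 and discharge.
- Definition, in timing terms: that converter fails if a listed intervention starts between the recurrence and discharge.

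**Test subjects.** All convert at minute 20. Discharge is assumed at minute 98 (8 minutes of dosing plus 90 minutes).

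| Case | Rate control started | AF recurrence | Listed rule | Definition |
|---|---|---|---|---|
| a | minute 5 | none | success | success |
| b | minute 5 | minute 40 | **failure** | **success** |
| c | never | minute 40 | success | success |
| d | minute 30 | minute 40 | **failure** | **success** |
| e | minute 45 | minute 40 | failure | failure |
| f | 10 minutes before dosing | minute 40 | success | success |

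The rules part in b and d only, and the listed rule is the stricter one both times. Cases a and c show that neither early rate control alone nor an untreated recurrence alone fails the subject; the combination does. Case d shows that the fault also covers rate control begun after conversion but before recurrence. Case f shows that treatment started before dosing plays no part.

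**Scale.** The denominator is all mITT subjects in the cohort, so each affected subject moves the proportion by 1/n.

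- Pooled MLS cohort (Cohort 2): Protocol 1.4 gives 27 analysed Part A subjects on 120 mg FlecIH-103, and Protocol 10.3 B plans 25 mITT subjects in Part B. 27 + 25 = 52 before Part C subjects are added. 1/52 = 1.9 points. At an assumed n of 100, 1/100 = 1.0 point.
- A smaller cohort, for scale: 1/25 = 4.0 points. The SAP does not give the sizes of Cohorts 1, 3 and 4.

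**Effect on the interval, with assumed counts.** At n = 52, 25 successes give 48.1% (95% Clopper-Pearson 34.0 to 62.4). One reclassified subject makes it 24/52 = 46.2% (32.2 to 60.5).

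**The case against.** The case for leaving the rule alone has several parts.

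- **Few subjects can be affected.** Misclassification needs conversion within 90 minutes, recurrence before discharge, rate control newly begun between T0 and that recurrence, and nothing afterwards. Protocol 5.4.1 B permits these drugs but does not show that they are started in that short interval. This stands; the count is unknown and may be zero.
- **The error is conservative and tests nothing.** This also stands. The endpoint is secondary, SAP 6.2 plans no formal testing in the final report, and the bias is downward only. It remains a mismatch between definition and code that section 10 does not declare.
- **Timing is only a proxy for need.** Rate control given after a recurrence for some other reason would still count as failure under a recurrence-anchored window. True, but that proxy at least respects the order of events in the definition. The present one does not.
- **The early window does useful work.** Because the list omits the no-alternative-therapy condition, the dosing-start window is the only item in the recurrence branch that catches cardioversion by drug or ECV before the index conversion. This is right, and it means that moving the window alone would open a gap.

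A reader might infer that background rate-control use in general depresses the result. The documents do not support that: only interventions started at or after initiation of dosing count. A reader might also take 4 points or more per subject as the effect on the main result. That figure belongs to a cohort of 25, whereas the SAP's main efficacy presentation pools Parts A, B and C.

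**Conclusion.** The point holds within these limits. The listed requirement in SAP 9.2.2.7 does not implement the endpoint defined in the same section and in Protocol 10.2.1.8 B. It misclassifies converters with an untreated recurrence who had rate control newly started after T0 and before that recurrence.

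The bias is downward, at about 1.9 points or less per affected subject in the pooled cohort and more in any smaller cohort. The pooled figure assumes that the 27 Part A subjects and the planned 25 Part B subjects all enter the mITT population. The number affected is not known and could be zero.

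The finding also rests on reading alternative therapy as treatment meant to convert the rhythm, as SAP 3.2 and 9.2.1 indicate. If rate control counted as alternative therapy, a subject given it between T0 and conversion would fail anyway, though case d would remain. The primary endpoint is untouched. The rule should be corrected because it is wrong as written and cheap to put right, not because a conclusion of the trial depends on it.

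**What to change.** Make both changes to the list in SAP 9.2.2.7 in one edit:

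1. In the recurrence branch, replace the period running from initiation of dosing to discharge with: *at or after the start time of the first AF recurrence and up to discharge*.
2. In the first requirement, after the 90-minute conversion condition, add: *without an alternative therapy (as for the primary endpoint)*. Cardioversion by drug or ECV before the index conversion then still fails the subject.

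Apply the same list to the repeat analysis in that section, which uses 90 minutes post dose. If the investigator's reason for an intervention is recorded, showing it in the listing would let a reader judge whether the recurrence required it.

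The cost is two phrases in the SAP, one changed date-time comparison, and reuse of the primary-endpoint flag. The first recurrence time already comes from the Core Laboratory or, failing that, the investigator (SAP section 6). The existing rule already needs intervention start times, so no new data are required.
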